1.2. Study Discontinuation

We will encourage subjects to continue enrollment in the study via follow-up visits regardless of the nature of discontinuation of the tPBM. At the end of the study, we will refer the subjects to their counselor and/or psychiatrist and will communicate clinical data upon signed authorization. If the CGI-S increases more than 2 points during the study, the subject will be counseled to start

or change to an FDA-approved medication treatment. If the CGI-S increases more than 5 points or if a subject becomes actively suicidal as per clinician judgment, termination from the study will be mandated. Subjects who are deemed actively suicidal and are in imminent danger will be escorted to Acute Psychiatric Service (the local psychiatric Emergency Department at Massachusetts General Hospital) for evaluation and subsequent hospitalization. If the subject is appropriate for outpatient monitoring, the subject will be followed with frequent appointments outside the study. Each subject will have the Investigator's contact information as well as instructions on how to call for emergency services, if needed.

If study participation is discontinued due to safety reasons, participants will receive three follow-up visits, while appropriate psychiatric follow up access is assured with their treating psychiatrist. If emergent suicidality were to occur during the course of the study, the supervising clinician will then directly assess the level of risk and take the appropriate action (including contacting treatment providers, working on a safety plan, arranging for emergency evaluation via an ER, calling 9-1-1, etc.). The clinician will document the actions taken, and it will be noted in the participant's file. Subjects who discontinue due to non-compliance with the protocol will receive a referral to treaters in the area.

A participant may withdraw consent at any time for any reason (e.g., lack of efficacy, adverse events, etc.). A subject may be withdrawn from the study by study staff at any time if any of the following conditions are met:

- Worsening of ATs, ADHD or current/emergent major psychiatric disorder.
- Subjects who experience intolerable adverse effects as determined by the PI.
- Emergent suicidality
- Pregnancy
- Failure to keep study appointments for more than 2 consecutive visits
- Failure to utilize the telemedicine platform
- Clinical judgment of the investigator

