Risk of Depression, Suicidality & Manic Switch: Worsening of depression and increased suicidality are possible complications of antidepressant treatments which could be prescribed to subjects with ASD and mood disorders. We will minimize this risk by selecting only subjects who do not present active suicidal ideation at screening. We will also discontinue any subject who develops active suicidal ideation during the course of the study and arrange for appropriate levels of care and standard treatment. Manic switches are possible adverse events and will be closely monitored during treatment as well. Regularly scheduled clinical study visits will allow early recognition of treatment-emergent suicidal ideation or prodromal hypomanic signs. Subjects who develop mania or hypomania will be discontinued and provided appropriate level of care.

Answering detailed questionnaires may create a mild degree of inconvenience for the subjects and will be monitored by study clinician.

Risks of Assessments/Questionnaires

Some questions may make subjects feel uncomfortable because of the nature of the question topics. Some questions ask about possibly sensitive information, including questions pertaining to alcohol and drug abuse. Subjects may refuse to respond to any questions they do not feel comfortable answering.

Adverse events and unanticipated problems will be reported to the PHRC according to current guidelines. We will follow and adhere to all guidelines as defined and outlined on the Partners Human Research Committee web site: http://healthcare.partners.org/phsirb/adverse_events.htm

Other Adverse Events Related to Study Treatment

Problems and side effects not listed above and not known at this time could occur. Subjects will be informed of any newly discovered risks as investigators come to learn of such knowledge, if applicable. At this time, there is no research that examines the long term effects of tPBM treatment. As such, the long-term effects of this treatment are unknown.

Safety Monitoring

The study subjects will undergo frequent clinical evaluations including depressive scores, concomitant medications, adverse events, and serious adverse events and unexpected device events will be recorded from study entry through completion. Additionally, doctors must monitor a subject's safety by asking the subjects frequently about the subject's own comfort during treatment application.

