If skin erythema is present, treatment will be suspended. Patients will be instructed to contact the study site principal investigator or a member of his staff at any time between visits concerning adverse events or worsening of symptoms. If at any study visit the subjects' clinical condition is significantly worsened from baseline (operationalized as the clinical global impression improvement score, CGI-I, of 6 or higher) or if a subject becomes actively suicidal with intent and/or plan, based on the C-SSRS scale and/or the clinical interview, the subject will be offered to start an antidepressant medication. If the subject were deemed at imminent danger as a result of suicidality, s/he would be discontinued from the study and referred to appropriate clinical treatment (see 4.7.3 Study Discontinuation).

Photobiomodulation for ASD in ADHD

The Principal Investigator ([name]) will have weekly meetings which will include study RAs; during these meetings calls they will discuss all Adverse Event reports to identify any safety concern, based on such concerns they will be able to decide temporary discontinuation of study enrollment, modifications of the study protocol, or to terminate the study.

Research assistants responsible for data collection and storage will be aware of and comply with all regulatory requirements related to adverse events. In the event that a patient becomes ill or is injured as a direct result of study participation, medical care will be made available. All adverse events (and device events) will be followed to resolution and reported to the MGH IRB as serious in the event that 1. they are unanticipated and possibly related to the study (same reporting as SAE) or 2. if they meet any one of the following criteria: Any fatal event, immediately life-threatening event, permanently or substantially disabling event, event requiring or prolonging inpatient hospitalization, or any congenital anomaly. This also includes any event that a study investigator judges to impose a significant hazard, contraindication, side effect, or precaution.

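### Safety Monitoring contradicts two other sections on removing an actively suicidal child, and the CGI-S termination rule can be met only by a move from 1 to 7

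*Combined protocol and SAP*

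**What the plan says.** Three places govern a child who becomes suicidal during the study.

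- Section 1.2, Study Discontinuation: "if a subject becomes actively suicidal as per clinician judgment, termination from the study will be mandated". A child suitable for outpatient monitoring is then seen at appointments outside the study. Later in the section a general list opens with "A subject may be withdrawn from the study by study staff at any time if any of the following conditions are met", and "emergent suicidality" is one of its entries.
- Risks and Discomforts, the paragraph on depression, suicidality and manic switch: "We will also discontinue any subject who develops active suicidal ideation during the course of the study", with suitable care arranged.
- Risks and Discomforts, Safety Monitoring: if the child is significantly worse than at baseline, or is actively suicidal with intent or a plan, "based on the C-SSRS scale and/or the clinical interview, the subject will be offered to start an antidepressant medication". The next sentence reads "If the subject were deemed at imminent danger as a result of suicidality, s/he would be discontinued from the study" and refers the reader to Study Discontinuation as 4.7.3.

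Two places govern clinical worsening. Section 1.2 counsels starting or changing to an FDA-approved medication if the CGI-S rises by more than 2 points, and mandates termination if it rises by more than 5. Safety Monitoring uses a different measure for significant worsening, "operationalized as the clinical global impression improvement score, CGI-I, of 6 or higher", and the response is the antidepressant offer. Section 1.2.1.1 gives the CGI-S a range of 1 to 7 and says the CGI is used for both ADHD and autistic traits (ATs).

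**The concern.** Staff need one answer for a 9- to 17-year-old who has suicidal intent or a plan but is not judged to be in imminent danger. Section 1.2 and the suicidality paragraph both take that child out of the study. Safety Monitoring, read as it stands, states an antidepressant offer and does not say that the child leaves. Staff working from it could keep treating and rating a child whom the other two places remove. The offer also needs more context than it is given, because the suicidality paragraph itself warns: "Worsening of depression and increased suicidality are possible complications of antidepressant treatments".

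On worsening, the only CGI-based mandatory stop should be one that can act on the children enrolled. If the required rise is larger than the scale allows from a child's starting score, the rule protects nobody at that score.

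**Working it through.** **Suicidality.** No arithmetic applies, so the rules are set side by side for active suicidality with intent or a plan and no imminent danger.

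| Place | Trigger | Stated action |
|---|---|---|
| Section 1.2, text | Actively suicidal, by clinician judgment | Termination mandated; outpatient follow-up outside the study where suitable |
| Suicidality paragraph | Active suicidal ideation | Discontinue, arrange care |
| Safety Monitoring | Actively suicidal with intent or a plan | Antidepressant offer; discontinuation stated for imminent danger |

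A child who meets the third trigger also meets the first two. If the first two are followed, that child has already left, and a separate discontinuation step at imminent danger has nothing to do. A tiered reading therefore does not reconcile the three.

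Two supporting checks:
- The C-SSRS is in none of the visit lists (screening, baseline, weeks 1 to 6, endpoint, week 10) and not in Table I. The clinical interview is the stated alternative.
- No section is numbered 4.7.3. The section with that title is 1.2.

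**Worsening.** Inputs: CGI-S takes the integers 1 to 7 (section 1.2.1.1); thresholds are more than 2 and more than 5 (section 1.2); entry requires SRS raw score ≥ 75 or CGI-AT severity ≥ 4 (Inclusion Criteria). Section 1.2 does not name the reference score, so the rise is taken from baseline.

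From baseline b the largest possible rise is 7 − b.
- More than 2 needs 7 − b ≥ 3, so b ≤ 4. From 4 only a score of 7 qualifies.
- More than 5 needs 7 − b ≥ 6, so b = 1, and only a score of 7 qualifies.

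The number of upward moves larger than k points is the sum over b of max(0, 7 − b − k):
- All upward moves (k = 0): 6 + 5 + 4 + 3 + 2 + 1 = 21.
- More than 2: 4 + 3 + 2 + 1 = 10.
- More than 5: 1.

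| Baseline | Upward moves | Rise > 2 | Rise > 5 |
|---|---|---|---|
| 1 to 3 | 6 + 5 + 4 = 15 | 4 + 3 + 2 = 9 | 1 |
| 4 to 7 | 3 + 2 + 1 = 6 | 1 (4 to 7) | 0 |
| All | 21 | 10 | 1 |

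These are counts of possible moves, not probabilities. Baselines 4 to 7 on the AT rating correspond to the CGI-AT entry route. A lower CGI-AT is possible for a child who enters on the SRS score alone, and no entry limit is set for the ADHD rating.

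**The case against.** The strongest defence is that the protocol already answers the central case. Section 1.2 mandates termination and provides for follow-up outside the study, and Safety Monitoring points to that section by title. A clinician could also terminate the child and offer medication. This shows what was probably intended, and it limits the harm. It does not remove the conflict: Safety Monitoring does not say that the child leaves, and its pointer has the wrong number and is attached to the imminent-danger sentence.

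Several stronger readings are tempting, and the documents do not support them.
- *Four different suicidality thresholds.* Section 1.2 and the suicidality paragraph are close to equivalent, and both require the child to leave. The discretionary list can be read as a wider general power that leaves the specific mandate intact. Safety Monitoring is the outlier.
- *Both CGI-S rules are out of reach.* The more-than-2 rule can be met from baselines 1 to 4. Low ADHD ratings are plausible, since the introduction describes participants with adequately treated ADHD.
- *Some children have no safeguard against worsening.* CGI-I of 6 or higher can be given from any baseline, and worsening is a listed ground for discretionary withdrawal.
- *No emergency route exists for remote visits.* Section 1.2 does speak of escorting a child to the hospital's emergency service although visits are remote, but its next paragraph gives remote steps. That is a minor wording point.
- *The two medication responses contradict each other.* An antidepressant may be an FDA-approved medication. The responses differ in wording without necessarily conflicting.

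**Conclusion.** The concern holds on two counts. First, Safety Monitoring contradicts section 1.2 and the suicidality paragraph for a child with active suicidality and intent or a plan who is not in imminent danger. The wrong section number and the unscheduled C-SSRS make it harder to resolve on the day. Second, the mandated stop at a CGI-S rise of more than 5 can be met by 1 of 21 upward moves. Counted from baseline, it cannot act on the AT rating for any child who entered with CGI-AT ≥ 4. If the rise were counted from a later, better score, it would still need a 1 followed by a 7.

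The counselling rule is weaker than it looks but usable: 10 of 21 moves overall, 1 of 6 from baselines 4 to 7, none from 5 to 7. Section 1.2 does not say whether the AT or the ADHD rating applies. The documents give no rate of suicidality or of CGI worsening, so no number of affected children is claimed. These are safety rules for minors that should be corrected. The point does not bear on the primary efficacy analysis.

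**What to change.** 1. Amend Safety Monitoring so that active suicidality leads to the mandatory discontinuation already required in section 1.2 and the suicidality paragraph. Add referral, any medication decision as part of that care, and the exit assessments listed under Withdrawal from the Study if feasible. Correct the cross-reference to section 1.2. State in that section's discretionary list that active suicidality is a mandatory ground.
2. Delete the C-SSRS reference so that the clinical interview governs. Scheduling the scale in Table I is the alternative, with a small added burden.
3. Replace the more-than-5 CGI-S stop with one that can be reached, using the CGI already collected at every visit: for example, CGI-I of 7 on either the AT or the ADHD scale. In place of the more-than-2 rule, use the existing CGI-I trigger of 6 or higher, with one stated response.

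The cost is protocol wording and an IRB amendment, and possibly a rare extra discontinuation, whose frequency cannot be estimated because no event rate is given.

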dependent variable will be raw score on the SRS-2 Total scale and our predictor will be study visit (continuous). Secondary measures of efficacy for the treatment of ATs will be the SRS-2 subscales which include Awareness, Cognition, Communication, Social Motivation, and Restricted Interests and Repetitive Behavior. These subscales will also be analyzed using mixed-effects linear RMs predicting subscale score from study visit (continuous). Safety and tolerability will be assessed by examining adverse events reported throughout the trial.

Secondary Objective: posits that tPBM will be effective in the treatment of ADHD with ATs. The measure of efficacy for this objective will be the ADHD-SC which is collected at baseline, midpoint, and endpoint. We will examine the change in ADHD-SC score over time using a mixed-effects linear RM. Our dependent variable will be ADHD-SC score and our predictor will be the study visit (continuous).

Accountability/Investigational Product Control

U.S. federal law and ICH Guideline E6 § 5.14 requires that all investigational medical devices be strictly controlled. All study devices must be kept in a secured area at the clinical sites in compliance with all applicable FDA (U.S. sites) regulations.

The Principal Investigators or designated study site personnel who verify the receipt of the devices/device accessories must complete the Device/Accessories Acknowledgment Form and fax a copy to Niraxx, Inc. Device Accountability and Acknowledgment Logs will be maintained at study site. These logs will list all equipment received, the receiving date, the serial number of each device. Study site personnel will initial the log each time the device is used. Niraxx device use will also be recorded on the appropriate CRF.

Malfunctioning devices and device accessories, including all components, will be returned to Niraxx, Inc. for investigation, at Niraxx, Inc. expense.

VI. RISKS AND DISCOMFORTS

All adverse events will be recorded from the time of Informed Consent through study completion, or termination. The Adverse Event CRF must be completed and submitted to the IRB, as required. Regulations for adverse event handling and reporting contained in the FDA and ICH Guidelines will be adhered to.

Consideration of Adverse Events will hereafter consist of Adverse Events, Serious Adverse Events, and Adverse Device Effects, including Anticipated Adverse Device Effects and Unanticipated Adverse Device Effects.

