- **Mild.** The Adverse Event is transient, requires no treatment, and does not interfere with the subject's daily activity.
- **Moderate.** The Adverse Event introduces a low level of inconvenience or concern to the subject and may interfere with daily activities, but is usually ameliorated by simple therapeutic measures.
- **Severe.** The Adverse Event interrupts the subject's usual daily activity and requires systematic therapy or other treatment.

If the Adverse Event is of such intensity in the Investigator's judgment that it warrants withdrawal from the study, the subject should be withdrawn from treatment. The subject should be given appropriate care under medical supervision until symptoms resolve.

The relationship of an Adverse Event to the study device or procedure will be graded as follows:

- **Unrelated.** The Adverse Event is not associated with the study device use.
- **Possible.** This causal relationship is assigned when the Adverse Event:
 - Follows a reasonable temporal sequence from device use,
 - Could have been produced by the subject's clinical state or other modes of therapy administered to the subject, or
 - Cannot be reasonably explained by known characteristics of the subject's clinical state.
- **Definite.** This causal relationship is assigned when the Adverse Event:
 - Follows a reasonable temporal sequence from device use;
 - Abates upon discontinuation of the treatment; and
 - Is confirmed by the reappearance of the Adverse Event on repeat exposure.

Serious Adverse Events

All Serious Adverse Events must be reported to the overseeing Institutional Review Board (IRB), FDA, and Niraxx, Inc as required.

If the Investigators are notified by Niraxx, Inc or its designee of any Serious Adverse Events that are considered to be Unanticipated Adverse Device Effects, the Investigators must notify his/her own IRB/EC as required.

Deaths

Deaths which must be reported to Niraxx Inc include all deaths while participating the study.

Withdrawals for Adverse Events

All Adverse Events which result in the subject's withdrawal from the study must be reported immediately by telephone to Niraxx Inc.

Photobiomodulation for ASD in ADHD

The Investigator may be asked to provide detailed follow-up information. The Investigator will determine the reportability of the event on a case-by-case basis, and will report to the appropriate regulatory authorities evaluating the study device as necessary.

Subject Disposition Criteria

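### The causality scale for adverse events cannot separate events with a competing cause from events without one: the two alternative-cause criteria under Possible cancel, and no grade lies between Possible and a Definite that needs re-exposure

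*Combined protocol and SAP*

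**What the plan says.** Reporting Procedures for All Adverse Events makes relationship to the device or procedure a mandatory attribute of every adverse event and defines three grades.

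- *Unrelated*: "The Adverse Event is not associated with the study device use". No criteria follow.
- *Possible*: three criteria. The first is "Follows a reasonable temporal sequence from device use", ending in a comma with no conjunction. The second is "Could have been produced by the subject's clinical state or other modes of therapy administered to the subject, or", which leads by its final word to the third, "Cannot be reasonably explained by known characteristics of the subject's clinical state".
- *Definite*: a temporal sequence, then "Abates upon discontinuation of the treatment; and" and finally "Is confirmed by the reappearance of the Adverse Event on repeat exposure". All three are required.

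Safety and tolerability is one of the two primary objectives (Specific Aims). The analysis text for it is one sentence: "Safety and tolerability will be assessed by examining adverse events reported throughout the trial" (Biostatistical Analysis, Primary Objective). Treatment is daily for 8 weeks (Devices and Dosing). Safety Monitoring says that treatment is suspended for erythema, and describes no restart procedure.

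**The concern.** In a single-arm, open-label trial no comparator supplies background rates. The causality grade is then one of the few tools for telling device effects from complaints that youth with ADHD, some of them on medication, would have anyway. A useful scale places an event with no other explanation above an event that has one. Here the criterion that should make this distinction is satisfied in both cases, and the only higher grade depends on re-exposure. Events that end treatment are of most interest for tolerability, and they are also the ones for which re-exposure may never occur. Any summary of device-related events built on this scale would be hard to interpret.

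**Working it through.** The plan states no figure to reproduce. The question is one of logic, so the definitions can be checked by listing every combination of the attributes they use.

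**Inputs** (all from the relationship grading in Reporting Procedures for All Adverse Events). Each attribute is yes or no:

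- T: reasonable temporal sequence from device use
- S: explained by the clinical state
- O: could be due to other therapy
- D: abates on stopping
- R: reappears on repeat exposure

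This gives 2^5 = 32 event profiles. The criteria are:

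- A = T
- B = S or O (another cause could have produced the event)
- C = not S (the clinical state does not explain the event)
- Definite = T and D and R

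**Step 1: the two alternative-cause criteria together.** B or C = (S or O) or (not S). This is true for every profile. B and C are near-opposites rather than exact opposites, because C does not mention other therapy, but their union is still everything.

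**Step 2: Possible under each reading.**

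| Reading | Condition | Profiles meeting Possible |
|---|---|---|
| Literal | A or B or C | 32 of 32, including the 16 with no temporal link |
| Charitable | A and (B or C) = A | 16 of 32, exactly those with a temporal link |
| All three required | T and O and not S | 4 of 32 |

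The third reading contradicts the printed 'or'. It would also confine Possible to events that the clinical state does not explain but other therapy might. Under either reading that respects the 'or', another explanation never changes the grade.

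**Step 3: what lies above Possible.** Of the 16 temporally linked profiles, Definite is met by 4 (D and R both yes, with S and O free: 2 × 2). The other 16 − 4 = 12 stay at Possible. Among the 16, another cause (S or O) is present in 3 × 4 = 12 and absent in 1 × 4 = 4. Definite takes 3 of the former and 1 of the latter. Possible therefore holds 12 − 3 = 9 profiles with a competing cause and 4 − 1 = 3 with none, under one label.

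**Step 4: overlap.** The 4 Definite profiles also meet Possible under the literal and charitable readings, and no rule says that the higher grade applies.

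These are counts of logical combinations. They are not event frequencies, and the documents contain nothing from which frequencies could be derived.

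**The case against.** The strongest reply is that the scale works better in use than on paper, and that little depends on it.

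- **Daily sessions supply re-exposure.** Warmth, discomfort or headache, all listed under Potential Adverse Events, can fade and return at the next session. A headache after every session that stops when treatment stops can meet all three Definite criteria. An event can also recur over several sessions before a subject is withdrawn, and the Flexible Titration Schedule allows holding or lowering the dose, so an adverse event need not end exposure. This stands. A reader might infer that nearly every device-related event must end as Possible, that every event leading to withdrawal is capped there, or that a report of no definitely related events is almost guaranteed. The documents support none of these. The cap applies only where treatment ends before any recurrence.
- **The temporal criterion is a judgement.** The word 'reasonable' calls for a view on plausible latency. A reader might infer that every on-treatment event qualifies because a session took place within the day, but no section sets that rule.
- **Events before first use.** Adverse events are recorded from consent (Risks and Discomforts), and on the literal reading even one that precedes any irradiation could be called Possible. That reading is strained: Unrelated plainly fits, and the date of onset must be recorded.
- **Consequences are contained.** All adverse events are documented whether or not attributed to the device, all serious events go to the IRB whatever their relatedness, and no planned analysis tabulates by grade. This stands too. Safety Monitoring treats events as serious when "they are unanticipated and possibly related to the study (same reporting as SAE", but that text does not cite the grading scale. If the grade were used there, a broad Possible would lean towards over-reporting, and adding a higher grade would leave the trigger largely unchanged.

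None of this answers the core defect. The protocol does not say whether recurrence at the next session is repeat exposure, or whether the gap between sessions is discontinuation, so the route to Definite is itself open to interpretation.

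**Conclusion.** The definitions should be rewritten. Possible reduces to a reasonable temporal sequence on the charitable reading and overlaps Unrelated on the literal one. With no intermediate grade, an event with good timing and no other explanation that ends treatment before recurring is graded the same as one with an obvious competing cause.

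The size of the problem cannot be expressed as a rate. The effect is limited to the grading and summary of device-related events under the primary safety objective. It does not reach the recording of adverse events, the reporting of serious events to the IRB, or any planned statistical test. The conclusion rests on taking the printed conjunctions as intended and on the absence, elsewhere in the protocol, of a rule for choosing between grades or defining repeat exposure. It is worth correcting because safety is a primary objective, there is no comparator, and the repair is cheap.

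**What to change.** Rewrite the relationship grades in Reporting Procedures for All Adverse Events so that they are mutually exclusive and exhaustive. Settle Unrelated first, then assign the highest remaining grade that is met.

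- **Unrelated**: no reasonable temporal sequence from device use, including onset before the first irradiation, or clearly due to another cause.
- **Possible**: reasonable temporal sequence, and the clinical state or other therapy could have produced the event.
- **Probable** (new): reasonable temporal sequence, and not reasonably explained by the clinical state or other therapy. Abatement on stopping supports this grade but is not required; otherwise an event with no other cause that persists after treatment stops would have no suitable grade.
- **Definite**: as now, with a statement of whether recurrence at a later daily session counts as repeat exposure.

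On the same 32 profiles this gives 16 Unrelated, 9 Possible, 3 Probable and 4 Definite (16 + 9 + 3 + 4 = 32), so each profile has one grade. Events judged clearly due to another cause would move from the 9 to Unrelated. The change concerns grading only and implies nothing about restarting treatment in any subject.

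In Biostatistical Analysis, state that events will be summarised as Probable or Definite and, separately, as Possible or higher.

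The cost is protocol wording and one extra response option on the adverse-event form. Some events will be graded as more strongly related than under the present text.
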